10.2. Appendix 2: Time & Events

10.2.1. Protocol Defined Time & Events

10.2.1.1. Schedule of Assessments Year 1 to End of Study

Protocol activity (visits ±1 week, except Weeks 2 and 4					Day 1	I through Week 52		
which are ±3 days) All assessments pre-dialysis unless otherwise specified (Note: All visit timings are relative to Day 1)	Screen Week -8	Run-in Week -4	Day 1 ¹³	Week 2	Full study visit Week 4, 16, 28, 40	Abbreviated study visit Week 8, 12, 20, 24, 32, 36, 44, 48	Week 52	Unscheduled ¹⁰
Informed consent (main study)	X ²²							
IRT system transaction ¹⁷	Х	Х	Х	Х	Х	Х	Х	Х
Subject reminder, inform site staff of changes in health ¹			Х				Х	
Check/confirm entry criteria	Х		Х					
History: medical, hospitalization, transfusion demography, height	Х							
Weight (pre- and post-dialysis for in-center HD subjects; between treatments for HHD; at study visits per standard of care for PD) and EDW	х	x	х	х	х	x	х	х
SBP/DBP, HR (pre- and post-dialysis for in-center HD subjects; between treatments for HHD; at study visits per standard of care for PD) (single readings unless otherwise indicated)	х	х	X (triplicate)	Х	x	x	X (triplicate)	Х
Kt/V _{urea} ¹⁸			Х		Х		Х	
ECG ²			X2				Х	
Ultrasound of kidneys and adrenal glands		X ¹⁶						
Placebo run-in or randomized treatment dispensing (start administration on date treatment dispensed) ¹⁹		X (placebo)	Х	X9	Х	х	Х	X9
Placebo run-in or randomized treatment compliance ¹⁹			X (placebo)	X ¹¹	Х	Х	Х	X ¹¹
Iron therapy, transfusions ³	Х	Х	Х	Х	Х	Х	Х	Х
Rescue medication(s) for Initial Intervention ^{3,4}					Х	Х	Х	
Females only: estradiol and FSH (if required)	Х							
FRP only: Serum pregnancy test 5,20		Х	Х		Х		Х	

200807

Protocol activity (visits ±1 week, except Weeks 2 and 4					Day 1	l through Week 52		
which are ±3 days) All assessments pre-dialysis unless otherwise specified (Note: All visit timings are relative to Day 1)	Screen Run-in Week -8 Week -4		Day 1 ¹³	Week 2	Full study visit Week 4, 16, 28, 40		Week 52	Unscheduled ¹⁰
HemoCue Hgb	Х	Х	Х	Х	Х	Х	Х	Х
Hematology ⁶	Х	Х	Х		Х	Hgb only	Х	Х
Clinical chemistry ⁶	Х		Х		Х		Х	Х
Ferritin, total iron, UIBC ⁶	Х		Х		Х		Х	
Hepcidin			Х		Х		Х	
HbA1c ⁷ , lipids (non-fasting)			Х				Х	
hsCRP, iPTH			Х		Wk 28		Х	
Storage biomarkers ²¹			Х		Wk 28		Х	
Hospitalization ³ , kidney transplant ³				Х	Х	Х	Х	Х
Non-serious AEs, SAEs, AEs of special interest, clinical events	X8	Х	Х	Х	Х	х	Х	Х
Review concomitant medications	Х	Х	Х	Х	Х	Х	Х	Х

200807

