- 16. Ultrasound of the kidneys and adrenal glands will be performed as early as 6 weeks prior to the Day 1 visit. If results of kidney and adrenal ultrasound require follow-up testing, then the run-in period can be extended by 1 additional week. A documented ultrasound of the kidneys within the 6 months prior to screening may be used to assess entry criteria,

200807

provided the size and cyst category has been reported. If a more sensitive imaging study [e.g., magnetic resonance imaging (MRI), computed tomography (CT)] has been performed within this timeframe and a report is available, this may be used in place of the ultrasound. See Protocol Section 7.4.10.

- 17. Treatment will be dispensed every 4±1 weeks; an IRT transaction will be required; perform randomized treatment compliance.
- 18. A historical Kt/Vurea measurement within the last 12 weeks can be used. If a Kt/Vurea measurement is not available, then a urea reduction ratio (URR) measurement is acceptable. Kt/Vurea and URR measurements are not required for daily HHD.
- 19. In circumstances where the new dose of randomized treatment cannot be dispensed on the day of the study visit, the new dose of randomized treatment can be dispensed at next HD treatment. For visits after Day 1, prior randomized treatment should be continued unless on dose hold, Hgb ≥12 g/dL. Compliance is deferred until randomized treatment is returned.
- 20. For Argentina ONLY: Pregnancy testing will be performed every 4 weeks for FRP as required by local law.
- 21. Biomarker samples will be stored for future analyses for all subjects, except if not permitted by IRB/EC or refused by subject.
- 22. Informed consent will be obtained prior to any study procedures.

200807

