10.2.1.2. Schedule of Assessments for Patient Reported Outcomes, Genetics and Sub-studies

Protocol Activity	Scre	ening		Day 1 through Week 208							
(visits ±1 week) (Note: All visit timings are relative to Day 1)	Week -8	Week -4	Day 1	Week 4	Week 8 & 12	Week 16, 20 & 24	Week 28	Week 32, 36, 40, 44, 48	Week 52	Week 100, 148, 208	End of Study
Patient Global Impression of Severity (PGI-S) ¹	Х		Х		х		Х		Х		
Patient Global Impression of Change (PGI-C) ¹					Х		Х		Х		
Short Form 36 (SF-36) ¹			Х		Х		Х		Х		
EuroQol 5 Dimension 5 Level Health Utility Index (EQ-5D-5L) and EuroQol Visual Analogue Scale (EQ-VAS) ^{1, 2}			х		х		Х		Х	х	Х
Healthcare resource utilization (subject reported)				Х	Х	Х	Х		Х	Х	X (& Follow up)
Genetics sample ³			Х								
ABPM sub-study (Appendix 12): Informed Consent	X4	X4									
Atrial fibrillation/flutter screening		X5									
24 hour ABPM		X6				X (Week 16)					
Record awake and sleep times		X7				X ⁷ (Week 16)					
PK sub-study (Appendix 13): Informed Consent			X8	X8	X8	X8	X8	X8	X8		
PK assessment				Х9	X9	X9	X9	X9	X9		

1. Subjects who are unable to or require assistance to read must not complete the questionnaires.

2. Only in selected countries. See Protocol Appendix 3.

3. Informed consent for optional Genetic research should be obtained before collecting a sample. To minimize potential study bias, the genetic sample should be collected on Day 1.

4. Informed consent for ABPM sub-study can be obtained at Week -8 or at the Week -4 visit prior to conducting any ABPM sub-study assessments.

5. Heart rate will be assessed prior to ABPM, subjects with irregular heart beat will undergo an ECG to assess if atrial fibrillation/flutter is present (see Protocol Section 12.12.3.3)

6. Baseline ABPM will be performed at any mid-week dialysis visit starting at Week -4 until 1 week prior to randomization (Day 1); the device will be returned at the next visit, which ideally is no later than 1 week prior to randomization to allow for QC of the ABPM.

7. Subject will record sleep and awake times during the ABPM session.

200807

- 8. Informed consent for PK sub-study can be obtained anytime from Day 1 (once the subjects is confirmed to have been randomized to daprodustat) till Week 52, i.e., last study visit where PK sampling can be obtained.
- 9. Blood samples will be collected at any single study visit from the Week 4 through Week 52 visit (i.e., PK is collected at one visit only, based on convenience for the subject/site).

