10.6.3.6. Dose Adjustment Scheme Endpoints

Dose Adjustment S	cheme Endpoints		
General			
•	assigns all randomized me specified in the pro	d treatment doses in accord otocol.	ance with the dose
• •	 it is possible for subjection unscheduled visits. 	ects to change randomized t	reatment doses at both
• Sites are instructed to complete an exposure record every time dosing instruction is received from the IRT, with the exception of re-dispensing situations where the subject is instructed to continue using the same randomized treatment.			
• Summary tables for some dose adjustment scheme endpoints may summarize subjects by the type of rhEPO treatment received (i.e., epoetin alfa, darbepoetin alfa). Since it is possible for subjects to switch from epoetin alfa to darbepoetin alfa during the study, these displays will include subjects who switch rhEPO treatments in both the epoetin alfa and darbepoetin alfa groups.			
Daprodustat Doses			
Sites will enter the dose of daprodustat into exposure records – the daily frequency will be auto- populated for this randomized treatment. The dose steps of daprodustat are shown below:			
	Total Daily Dose	How Administered	

200807

Dose A	djustment Scheme Endpoi	nts
	1 mg	single 1 mg tablet
	2 mg	single 2 mg tablet
4 mg		single 4 mg tablet
6 mg		single 6 mg tablet
	8 mg	single 8 mg tablet
	10 mg	single 10 mg tablet
	12 mg	two 6 mg tablets
	16 mg	two 8 mg tablets
	24 mg	three 8 mg tablets
Epoetin	Alfa Doses	
dose ste	eps of epoetin alfa (including	cy of each dose of epoetin alfa into exposure records. The the corresponding total weekly doses) are shown below:
	Total Weekly Dose	Dose and Frequency
	1500	1500 U once a week
	2000	2000 U once a week
	3000	3000 U once a week
	4000	4000 U once a week
	5000	5000 U once a week
	6000	6000 U once a week
	8000	8000 U once a week
	10000	10000 U once a week
	12000	4000 U 3 times a week
	15000	5000 U 3 times a week
	18000	6000 U 3 times a week
	21000	7000 U 3 times a week
	24000	8000 U 3 times a week
	27000	9000 U 3 times a week
	30000	10000 U 3 times a week
	36000	12000 U 3 times a week
	42000	14000 U 3 times a week
	48000	16000 U 3 times a week
	60000	20000 U 3 times a week
	oetin Alfa Doses	
	•	cy of each dose of darbepoetin alfa into exposure records. Including the corresponding total 4-weekly doses) are shown
Ŀ	Total 4-Weekly Dose	Pre-filled Syringe Dose and Frequency
L		

Dose Adjustment Scheme	Endpoints			
30 µg	30 µg every 4 weeks			
40 µg	40 µg every 4 weeks			

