10.13.3. Pharmacokinetic Parameters

10.13.3.1. Deriving Pharmacokinetic Parameters

- Refer to Appendix 5: Data Display Standards & Handling Conventions (Section 10.5.3 Reporting Process & Standards).
- The pharmacokinetic parameters of parent GSK1278863, and metabolites (GSK2391220 (M2), GSK2506104 (M3), and GSK2531401 (M13)) will be calculated by programming methods.
- All calculations of non-compartmental parameters will be based on actual sampling times.
- Pharmacokinetic parameters described in Table 17 will be determined from the plasma concentration-time data, as data permits.

Parameter	Parameter Description
GSK1278863,	GSK2391220 (M2), GSK2506104 (M3) and GSK2531401 (M13)
tmax	Time to reach Cmax, determined directly from the concentration-time data.
Ctau	Observed concentration at dosing interval (tau=24 h, predose sample)
Cmax	Maximum observed concentration, determined directly from the concentration-time data.
GSK1278863	
Avg Dose EP TIR	The average daily GSK1278863 dose when the subject is on-treatment and in target Hgb range during the evaluation period (EP) Weeks 28-52 (See Section 10.6.3.1). Evaluable Hgb values are used to determine time in range. Subjects who permanently stop randomized treatment before the beginning of the EP, and subjects who have 0% time in range (e.g., subjects who have an evaluable Hgb below or above range for the entire EP) will have a missing value for this parameter.
Avg Dose EP	The average daily GSK1278863 dose when the subject is on-treatment during the EP.
Dose at first MACE	The daily GSK1278863 dose at the time of the subject's first on-treatment adjudicated MACE. If the subject does not have an on-treatment adjudicated MACE, this value is missing.
Final Dose for Subjects without MACE	For subjects without an on-treatment adjudicated MACE, this is the subject's final GSK1278863 dose during the study.
Dose at first MACE++	The daily GSK1278863 dose at the time of the subject's first on-treatment adjudicated MACE++ (defined as the first adjudicated MACE, hospitalization for heart failure, or thromboembolic event) If the subject does not have an on-treatment adjudicated MACE++, this value is missing.
Final Dose for Subjects without MACE++	For subjects without an on-treatment adjudicated MACE++, this is the subject's final GSK1278863 dose during the study.
Ctau/1mg Dose	Ctau extrapolated to 1mg dose: Observed Ctau divided by dose administered on the PK day

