Table 17Derived Pharmacokinetic Parameters for GSK1278863, and/or
GSK2391220 (M2), GSK2506104 (M3) and GSK2531401 (M13)

Parameter	Parameter Description
Ctau/Avg Dose EP TIR	Ctau extrapolated to average dose during EP TIR: Ctau/1mg multiplied by the average daily GSK1278863 dose when the subject is on-treatment and in target Hgb range during Weeks 28-52 (see Section 10.6.3.1). Evaluable Hgb values are used to determine time in range.
Ctau/Avg Dose EP	Ctau extrapolated to average dose during EP: Ctau/1mg multiplied by the average daily GSK1278863 dose during the EP.
Ctau/Dose at first MACE	Ctau extrapolated to dose at first on-treatment adjudicated MACE: Ctau/1mg multiplied by the daily GSK1278863 dose at the time of the subject's first on-treatment adjudicated MACE.
Ctau/Final Dose for subjects without MACE	For subjects without an on-treatment adjudicated MACE, this is the subject's Ctau/1mg multiplied by the subject's final daily GSK1278863 dose during the study.
Ctau/Dose at first MACE++	Ctau extrapolated to dose at first on-treatment adjudicated MACE++: Ctau/1mg multiplied by the daily GSK1278863 dose at the time of the subject's first on-treatment adjudicated MACE++.
Ctau/Final Dose for subjects without MACE++	For subjects without an on-treatment adjudicated MACE++, this is the subject's Ctau/1mg multiplied by the subject's final daily GSK1278863 dose during the study.
Cmax/1mg Dose	Cmax extrapolated to 1mg dose: Observed Cmax divided by dose administered on the PK day
Cmax/Avg Dose EP TIR	Cmax extrapolated to average dose during EP TIR: Cmax/1mg multiplied by the average daily GSK1278863 dose when the subject is on-treatment and in target Hgb range during Weeks 28-52 (see Section 10.6.3.1). Evaluable Hgb values are used to determine time in range.
Cmax/Avg Dose EP	Cmax extrapolated to average dose during EP: Cmax/1mg multiplied by the average daily GSK1278863 dose during the EP.
Cmax/Dose at first MACE	Cmax extrapolated to dose at MACE: Cmax/1mg multiplied by the daily GSK1278863 dose at the time of the subject's first on-treatment adjudicated MACE.
Cmax/Final Dose for subjects without MACE	For subjects without an on-treatment adjudicated MACE, this is the subject's Cmax/1mg multiplied by the subject's final daily GSK1278863 dose during the study.
Cmax/Dose at first MACE++	Cmax extrapolated to dose at MACE++: Cmax/1mg multiplied by the daily GSK1278863 dose at the time of the subject's first on-treatment adjudicated MACE++.

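### Ctau/1mg divides a pre-dose trough by the dose taken on the PK day, which gives a wrong value for any subject who starts a changed dose that day

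*SAP*

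**What the plan says.** All references are to the SAP.

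- **Trough.** Table 17 in 10.13.3.1 describes Ctau as "Observed concentration at dosing interval (tau=24 h, predose sample").
- **Normalisation.** The same table gives "Ctau extrapolated to 1mg dose: Observed Ctau divided by dose administered on the PK day". Cmax has the same divisor: "Cmax extrapolated to 1mg dose: Observed Cmax divided by dose administered on the PK day".
- **Carry-through.** Each of the other six Ctau extrapolations is Ctau/1mg times a dose, for example "Ctau extrapolated to average dose during EP: Ctau/1mg multiplied by the average daily GSK1278863 dose during the EP". The remaining five use the average dose while in range during the evaluation period, the dose at first MACE or first MACE++, and the final dose for subjects without MACE or without MACE++.
- **Sampling day.** Footnote 9 of 10.2.1.2: "Blood samples will be collected at any single study visit from the Week 4 through Week 52 visit".
- **Start of a dispensed dose.** The dispensing row in 10.2.1.1 reads "randomized treatment dispensing (start administration on date treatment dispensed"). Its footnote 19 covers visits where same-day dispensing is not possible: "the new dose of randomized treatment can be dispensed at next HD treatment". The prior treatment is meanwhile continued unless the subject is on a dose hold.
- **Dose data.** 10.6.3.6: "Sites will enter the dose of daprodustat into exposure records", with the daily frequency filled in automatically. That section lists the dose steps and defines the most recent dose prior to a visit separately from the dose assigned at it. 10.6.1 confirms that a zero dose is possible.

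**The concern.** With once-daily dosing, a sample drawn before the day's tablet measures what remains of the previous day's dose. Dividing it by the dose taken after the sample is harmless only when the two doses are equal, and Table 17 sets no such condition. PK visits are ordinary dispensing visits, at which the IRT may assign a new dose that starts the same day.

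Ctau/1mg is the common multiplier for all the extrapolated trough exposures, so an error in it passes unchanged into each of them. They are summarised and listed under Table 16. They also supply the exposure axis for three of the eight displays in Table 18: percent time in range, Hgb change, and the MACE/MACE++ boxplot. Section 10.13.4 names the exposure-response relation as the main aim of the analysis. Because dose changes follow Hgb, the error could also be related to response.

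**Working it through.** The SAP gives no figure to reproduce, so the check is algebraic.

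**Inputs**
- Ctau is a pre-dose sample with a 24 h interval (Table 17), and dosing is daily (10.6.3.6).
- Divisor: the PK-day dose (Table 17).
- Dose steps: 1, 2, 4, 6, 8, 10, 12, 16, 24 mg (10.6.3.6).
- Assumption: steady-state troughs proportional to dose. The SAP's own linear extrapolation makes the same assumption.

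**Formula.** Let *c* be the trough per mg, *P* the previous dose and *N* the dose taken on the PK day.
- Observed Ctau = *c* × *P*
- Intended Ctau/1mg = *c* × *P* / *P* = *c*
- Ctau/1mg as written = *c* × *P* / *N*
- Error factor = *P* / *N*; relative error = *P* / *N* − 1

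**One-step changes taken on the PK day**

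| Step (mg) | Increase: factor | Error | Decrease: factor | Error |
|---|---|---|---|---|
| 1 and 2 | 1/2 = 0.500 | −50.0% | 2/1 = 2.000 | +100.0% |
| 2 and 4 | 2/4 = 0.500 | −50.0% | 4/2 = 2.000 | +100.0% |
| 4 and 6 | 4/6 = 0.667 | −33.3% | 6/4 = 1.500 | +50.0% |
| 6 and 8 | 6/8 = 0.750 | −25.0% | 8/6 = 1.333 | +33.3% |
| 8 and 10 | 8/10 = 0.800 | −20.0% | 10/8 = 1.250 | +25.0% |
| 10 and 12 | 10/12 = 0.833 | −16.7% | 12/10 = 1.200 | +20.0% |
| 12 and 16 | 12/16 = 0.750 | −25.0% | 16/12 = 1.333 | +33.3% |
| 16 and 24 | 16/24 = 0.667 | −33.3% | 24/16 = 1.500 | +50.0% |

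**Carry-through.** For any later dose *D*, the extrapolated value as written is (*c* × *P* / *N*) × *D*, against the intended *c* × *D*. The ratio is again *P* / *N*, so all six downstream parameters have the same error.

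**Special cases**
- No dose change, or a new dose deferred under footnote 19 with the prior dose taken that day: *P* = *N*, the factor is 1, and there is no error.
- Hold before the PK visit: *P* = 0, so a trough with no dose behind it is divided by a real dose. The result cannot be interpreted.
- Hold starting on the PK day: *N* = 0 or missing, so the value is undefined.

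**Cmax.** The PK-day dose is the right divisor as long as the peak is observed after that dose.

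**The case against.** The best counter-argument is that the mismatch may never arise. The PK population in 10.13.1 is limited to subjects whose additional PK eligibility was confirmed, and the SAP does not define that eligibility. Sub-study procedures sit in a protocol appendix that is not at hand. A stable-dose condition, or an instruction to take existing supply on the sampling day, would make the two doses equal. This stands as a limit on how many subjects are affected. It does not make the derivation correct as written, because Table 17 neither states the condition nor refers to one.

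Footnote 19 of 10.2.1.1 also stands. A change assigned at the visit is not always a change taken that day, so it would be too broad to say that every subject with a dose change at the PK visit has a wrong value.

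The consequences are limited as well. No entry in Table 16 or Table 18 is marked as a formal statistical analysis, parallel Cmax displays are planned, and the largest percentages apply only to changes among 1, 2 and 4 mg.

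A reader might infer that the error creates a spurious exposure-response relation and distorts the MACE boxplots. The SAP does not support that. The error depends on the dose change at one visit between Week 4 and Week 52, whereas the Hgb outcomes are taken over Weeks 28 to 52 under titration to target. A link with response is possible, most directly when the PK visit falls within those weeks, but its net direction cannot be derived. For MACE and MACE++ no direction can be established at all.

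**Conclusion.** The derivation rule for Ctau/1mg is wrong as written, but only for PK sub-study subjects who actually start a changed daprodustat dose on the PK day. For them the seven dose-extrapolated Ctau values (Ctau/1mg and the six built on it) are 17% to 50% too low after a one-step increase, and 20% to 100% too high after a one-step decrease. Holds on either side of the sample give uninterpretable or undefined values. These sizes assume dose-proportional, steady-state troughs and are per affected subject. No effect on the sub-study as a whole can be given, because the share affected is not stated and could be nil.

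The point does not reach observed Ctau, the Cmax parameters, or any co-primary, principal secondary or other multiplicity-controlled result. It is a minor-to-moderate correction to exploratory PK/PD summaries and plots.

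**What to change.** In Table 17, define Ctau/1mg as observed Ctau divided by the last daprodustat dose taken before the pre-dose sample, drawn from the exposure records. Set it to missing if that dose was zero or unknown. Keep the PK-day dose as the divisor for Cmax/1mg. The definition of the most recent dose prior to a visit in 10.6.3.6 is a close starting point. The six downstream parameters then need no change of wording.

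If the protocol already requires an unchanged dose around PK sampling, a sentence in Table 17 saying so would settle the matter instead.

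The cost is one line of SAP text and one programming change, using data already collected. Subjects on a hold before the PK visit lose an extrapolated Ctau that had no usable meaning. The change concerns the derivation only and implies nothing about how doses are assigned.

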10.13.4. Pharmacokinetic / Pharmacodynamic Analyses

- The primary goal of this analysis is to characterize the pharmacokinetic/pharmacodynamic relationship of parent GSK1278863 and efficacy and safety endpoints in the "Pharmacokinetic" population from this study.
 - The influence of subject demographics and baseline characteristics, including disease activity in this population may be investigated.
- A summary of the planned population pharmacokinetic/pharmacodynamic analyses are outlined below:
 - Relationships between drug exposure and selected efficacy, MACE and MACE
 ++ events will be explored and characterized as data permit. The exposure will be estimated on the sparse PK collected in a sub-set of the study population. The data may be dose- extrapolated to the dose administered during the PK collection period. Any changes to the proposed analyses would be described in the CSR.

Table 18Overview of Planned Pharmacokinetic / Pharmacodynamic Analyses
for GSK1278863

Parameter			Un	trans	formed	k		Log-Transformed						
		Stats		Sum	mary	Indiv	vidual	Stat	s Ana	lysis	Sum	mary	Indiv	vidual
	_A	nalys	is	L	-									
	T	F	L	T	F	F		T	F	L	Т	F	F	L
GSK1278863	1	1	T	1			1		1	1				
Scatter plot of % Time														
Evaluable Hgb in Range						Y								
during EP vs. Avg Dose EP TIR														
Scatter plot of Evaluable														
Hgb Change from						Y								
Baseline during EP vs.						•								
Avg Dose EP														
Scatter plot of % Time														
Evaluable Hgb in Range						Y								
during EP vs. Ctau/Avg Dose EP TIR														
Scatter plot of														
Evaluable Hgb Change														
from Baseline during						Y								
EP vs. Ctau/Avg Dose														
EP														
Boxplot of Ctau/Dose at														
on-treatment MACE or														
MACE++ by subjects with						Y								
or without on-treatment														
MACE or MACE++														
Scatter plot of % Time														
Evaluable Hgb in Range						Y								
during EP vs. Cmax/Avg														

200807

Parameter		Untransformed								Log-Transformed						
		Stat	S	Sum	mary	Indiv	vidual	Stat	s Ana	lysis	Sum	mary	Indiv	vidual		
	A	naly	sis													
	Т	F	L	Т	F	F	L	Т	F	L	Т	F	F	L		
Dose EP TIR																
Scatter plot of																
Evaluable Hgb Change						v										
from Baseline during EP						I										
vs. Cmax/Avg Dose EP																
Boxplot of Cmax/Dose at																
on-treatment MACE or																
MACE++ by subjects with						Y										
or without on-treatment																
MACE or MACE++																

NOTES :

• T = Table, F = Figure, L = Listings, Y = Display generated.

• Stats Analysis = Represents TFL related to any formal statistical analyses (i.e. modelling) conducted.

• Summary = Represents TFL related to any summaries (i.e. descriptive statistics) of the observed raw data.

• Individual = Represents FL related to any displays of individual subject observed raw data.

